### 10.2.5 Adverse events of special interest

An AE of special interest is defined by potential drug-induced liver injury (PDILI) SMQ (see Appendix 13.6).

# 10.3 Clinical laboratory evaluations

Actual values and changes from baseline of laboratory parameters (hematology and serum chemistry including iPTH and lipids) will be descriptively summarized at each available time point. In addition, last value, minimum value during treatment, and maximum value during treatment will be presented. End of treatment will be defined as last visit of Month 6 during DBPC period or Month 12 during OL period (defined in Section 3.2.4.2 and Section 3.2.4.3) not including the FU visit and during treatment for the minimum and maximum calculation will also exclude the FU visit.

Shift tables from Baseline to each post-Baseline time point will be presented. In addition, shift tables regarding the normal range at end of treatment, minimum and maximum shift at any time will also be produced for each hematology and biochemistry laboratory parameter. The shifts will be categorized using L (low), N (normal), H (high), missing, and total.

Graphs showing central tendency (median) and dispersion (interquartile range) of the absolute values and percent changes from baseline by visit will also be provided for the following laboratory parameters:

- calcium corrected by albumin
- phosphorus
- alkaline phosphatase.

# 10.3.1 Potential drug-induced liver injury and potential Hy's Law evaluation

The count and percentage of subjects with potential drug-induced liver injury (PDILI) will be tabulated at baseline and on study. For the primary analysis, all on-study visits up to Month 6 will be used, for final analysis all on-study visits with available values will be used. The following endpoints will be applied.

Confidential Page 42 of 89

A table will be produced to summarize potential Hy's Law cases. The following two endpoints will be calculated:

Incidence of subjects with

- [AST  $\geq 3x$ ULN or ALT  $\geq 3x$ ULN] and Total Bilirubin  $\geq 2x$ ULN
- [AST ≥3xULN or ALT ≥3xULN] and Total Bilirubin ≥2xULN in the absence of ALP ≥2xULN

In order to meet either of the above criteria, a subject must experience the elevation in bilirubin and ALT or AST (and the absence of ALP elevation, if applicable) at the same visit. For example, a subject who experiences a  $\ge 2$  x ULN elevation of bilirubin at one visit and a  $\ge 3$ xULN elevation in ALT (or AST) at a subsequent visit has not fulfilled the Hy's law criteria.

# 10.4 Vital signs, physical findings, and other observations related to safety

### 10.4.1 Vital signs

The following vital signs variables should be summarized: systolic blood pressure (mmHg), diastolic blood pressure (mmHg), body temperature (°C) and pulse rate (beats/min). The observed value and change from Baseline value for each vital sign variable by treatment group and visit will be summarized. A by-subject listing of all vital signs data will be provided. This listing should be presented by treatment group and will include: center, subject identifier, age, sex, race, weight, visit, vital sign variable and result.

### 10.4.2 Physical examinations

Abnormal results of the physical examination together with details of abnormalities: abnormality clinically significant or not, will be listed by subject and visit.

# 10.4.3 Height and Weight

Descriptive statistics of actual values and changes from Baseline in body weight, and BMI will be presented by scheduled visit will be summarized using the SS.

# 10.4.4 Electrocardiograms

ECG data will be analyzed by treatment group and visit for SS.

A summary of the number and percentage of subjects with normal, abnormal not clinically significant and abnormal clinically significant ECG results at all applicable visits will be provided.

The following ECG variables will be summarized descriptively (absolute values and change from Baseline) by visit: QTcF, RR, PR, QRS and QT.

A by-subject listing of all 12-lead ECG data will be provided.

#### 13 **APPENDICES**

#### 13.1 Alternative osteoporosis therapy (licensed drugs only)

Potential alternative osteoporosis therapies (licensed drugs only) are including but not limited to:

.ogen

.omonal ablation therapy
Active vit D and analogs
Chinese herbal medicine for treating osteoporosis (including but not limited to TFRD, ICA)
2nts who take any alternative osteoporosis therapy that listed above, will be reviewed and rmed by UCB medical team within each DEMs. A finalized list will be provided printing the study. orosis ther and DEM Patients who take any alternative osteoporosis therapy that listed above, will be reviewed and confirmed by UCB medical team within each DEMs. A finalized list will be provided prior to

Confidential

#### Definitions of adjusted p-values for BMD endpoints 13.2

Test ID Endpoint	Endpoint	Raw p- value	Adjusted p- value
1	Lumbar spine BMD percent change from Baseline at 6 months	p1	pl
2	Total hip BMD percent change from Baseline at 6 months	p2	Max (p1, p2)
3	Femoral neck BMD percent change from Baseline at 6 months	р3	Max (p1, p2, p3)
90chiu	Total hip BMD percent change from Baseline at 6 months  Femoral neck BMD percent change from Baseline at 6 months  College of the college of	Jaliati	

Confidential Page 47 of 89

### 03 Mar 2023 OP0002

# 13.3 Fracture Risk Assessment Tool: 10-year Probability of Major Osteoporotic Fracture (FRAX)

and we ger probabe a high fracture a new or additionally culation include sex and current tobacco smoking, a causes of secondary as daily. FRAX is a computer-based algorithm (http://www.shef.ac.uk/FRAX) that provides country/ethnicity-specific models for the assessment of fracture probability in men and women a major osteoporotic fracture (hip, clinical spine, forearm or humerus) or of a hip fracture alone. BMI, a historical fragility fracture, parental history of hip fracture, current tobacco smoking, ever

Confidential Page 48 of 89

### 13.4 Multiple Imputations for BMD endpoints

First, a repeated measures Gaussian model will be fitted to the data using a Bayesian approach, with non-informative priors for the mean and variance-covariance matrix to provide a joint posterior for the parameters in this model. The repeated measures Gaussian model will include separate mean profiles for each treatment group and the same covariates as those in the primary ANCOVA analysis.

Independent samples will then be drawn from the posterior distributions for the mean and variance-covariance matrix to provide inputs into an imputation model. For each subject with missing data, these sampled values of the parameters for mean vectors and the variance-covariance matrices specify a joint distribution for their observed and unobserved outcome data.

Missing post-baseline BMD will be modelled under missing at random assumption. The ANCOVA model as in primary analysis will include fixed effects for treatment (two levels), Baseline BMD value, machine type at baseline, region, age strata group (stratification factor), and interaction of Baseline BMD value and machine type at baseline as independent variables.

The MI-MAR method will be applied as follows based on raw values:

- Step 1: Any observation after date of ICEs will be set to missing.
- Step 2: Create a dataset, one for each treatment group, of study participants with observed values and those needing estimation by multiple imputation. For the imputation step, missing values will include non-monotone missing values (ie, intermittent missing values between completed assessments) and monotone missing values (ie, where all study participant data is missing after a given time point).
  - Step 2a: First, the intermittent missing values in each dataset will be imputed using the MCMC method with multiple chains, monotone missing data imputing pattern, and non-informative priors for all parameters. Unless specified differently, the first 200 iterations will not be used (the 'burn-in' option). A total of 100 sets of imputations will be performed. The seed used for these imputations will be 2022 and all other multiple imputation procedures described in this SAP will use this same seed as well.

The resulting 100 imputed data sets will have a monotone missing data pattern and will be imputed using a method for monotone missingness:

- Step 2b: For monotone missing data, monotone regression will be used to impute missing data. A separate regression model is estimated for each variable with missing values (ie, measurement at each time point). Based on the resulting model, a new regression model is then drawn and is used to impute the missing values for the variable. Since the data set has a monotone missing data pattern, the process is repeated sequentially for variables with missing values. The procedure will be based on the 100 imputed datasets generated from the MCMC procedure and will be performed by Imputation.
- Step 2c: If an imputed value falls outside of the pre-defined range of values for the given variable, the value will be truncated to be within the predefined range of values for the endpoint of interest.

The SAS® PROC MI procedure will be used for the imputation.

Confidential Page 49 of 89

Romosozumah

The visits to include in the MCMC and monotone regression steps will be the same, and will correspond to all data available at the time of the analysis, as specified below:

- For dry-runs conducted prior to the Month 6 analysis, all weeks up to Month 6 will be included,
- For the Month 6 analysis, all weeks up to Month 6 will be included,
- For the final analysis, all weeks up to Month 12 will be included.

The stratification factors (age strata group) may be dropped from the imputation model to facilitate model convergence if required (and this holds true for all imputation models). The post-Baseline values will need to be specified in chronological order in the imputation model so that the SAS® PROC MI imputes variables from left to right (ie, the Month 6 value will be first) imputed using regression based on Month 3, and then the Month 12 value will be imputed using regression based on Month 3 and Month 6 values, etc.).

The resulting datasets for each treatment arm will be combined into one complete dataset based on each of the 100 imputations (containing 100 times the number of study participants analyzed).

The imputation model based on the MCMC method for intermittent missing values will only allow multivariate normal variables. Therefore, region which has 3 levels will be re-coded as indicator variable:

One indicator variable (region1) will be defined as 0 for regions other than North and 1 for North. Two more indicator variables (region2 and region3) will be defined similarly replacing North with Eastern and South respectively. In the VAR statement of the imputation model, the indicator variables will be ordered as follows: region1 region2 and region3. In the eventuality that two regions required to be pooled due to a low percentage of study participants randomized in one region, the indicator variables defined above will be revised accordingly.

- One indicator variable will be defined for the age stratification variable: will be coded as 1 for <75 years and 0 for  $\ge$ 75 years.
- One indicator variable will be defined for the machine type at baseline variable: will be coded as 1 for Hologic and 0 for Lunar.

To maintain consistency with the MCMC method for intermittent missing values, these indicator variables will also be used in the monotone regression step for monotone missing values and treated as continuous variables.

- Step 3, the 100 imputed datasets from Step 2 will be combined, and simple means and standard errors will be calculated using Rubin's rules (via SAS® PROC MIANALYZE). For calculation of other descriptive statistics (median, minimum and maximum), Rubin's rules do not apply. Multiple imputation estimates will be computed by calculating arithmetic means of the estimates from the multiple repetitions of the imputation algorithm. Thus, for median, minimum and maximum the following approach will apply:
  - The data will be summarized by treatment, visit and imputation and the summary statistics will be computed.
  - Results will be summarized by taking the mean value of each summary statistic at each visit across all imputations.

Confidential Page 50 of 89  The number of decimal places will remain the same as the original for display purposes (ie, if the mean was presented to 1 decimal place, the mean of the means will also be presented to 1 decimal place).

In Step 3, the analysis will be done on the percentage change from Baseline, and the model will be an ANCOVA model with treatment group and the same covariates as those in the primary ANCOVA analysis.

In Step 5, the results obtained from the 100 ANCOVA analyses in Step 4 (ie, the Least Square Means for the treatment difference and the 95% CI for the contrasts) will be combined with Rubin's rules. Pseudo SAS codes for the sensitivity ANCOVA model of the endpoint as follows:

```
/***** for intermittent missing values ******/
PROC MI data=xxx NIMPUTE = 100 seed=xxx NOPRINT OUT=xxxx min=0 max=1;

BY trtp;

VAR type agegp region1 region2 base aval_m3 aval_m6;

MCMC CHAIN=multiple IMPUTE = monotone;

run;

/******* for monotone missing values *********/
proc mi data=xxx seed=xxx nimpute=1 NOPRINT out=xxxx;
var agegp trtp region machinetype base aval m3 aval m6;
class agegp trtp region machinetype
MONOTONE REGRESSION
BY imputation;
run;
PROC MIXED DATA
         BY imputation
         CLASS trtp type region agegp;
         MODEL pchg=base trtp type agegp region base*type;
         LSMEANS trtp / om cl stderr pdiff;
       ods output LSMeans=LMS Diffs=DIFF;
 *** MIANALYZE;
proc sort data=DIFF; by imputation; run;
```

This document cannot be used any extensions of variations thereof.

Confidential

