# 8.1 Statistical analysis of the primary efficacy variable

# 8.1.1 Primary analysis of primary efficacy variable

Primary analysis of Primary efficacy endpoint

Estimands's attributes to be considered for the evaluation of the primary endpoint

(1) Target Population: Postmenopausal Chinese women with osteoporosis meet the inclusion and exclusion criteria

Confidential Page 31 of 89

- (2) Treatment: Romosozumab or PBO for 6 months
- (3) Endpoint: percentage change from baseline in BMD at lumbar spine at end of DBPC period (month 6).
- (4) Intercurrent Events (ICEs) and strategies to handle ICEs:
  - (a) ICE #1: treatment discontinuation not due to COVID-19 will be handled by treatment policy strategy
  - (b) ICE #2: alternative osteoporosis therapy will be handled by treatment policy strategy.
  - (c) ICE #3: treatment interruption and impacted BMD data (missing or out of visit window) due to COVID-19 will be handled by hypothetical strategy
- (5) Population level outcome: difference of least square (LS) means for Romosozumab and PBO

ICE #1 Treatment discontinuation not due to COVID-19 and ICE#2 use of alternative osteoporosis therapy is rare (not expected to happen frequently). They will follow treatment policy strategy which align with ITT principle. The treatment policy strategy will include all available data observed at Month 6 regardless of the occurrence of intercurrent events. This means the analysis includes on- and off-treatment values collected after study participants prematurely discontinued study treatment but agreed to remain on the study and continued to attend visits and provide assessments at those visits or data after alternative/prohibited medication administrated. Those observed values will be analyzed according to the study participant's randomized treatment.

During COVID-19 pandemic, study procedures (i.e. IMP administration and BMD assessment) are heavily impacted by sites close, participants quarantined or partially lock down. Thus, treatment was interrupted, or BMD assessment could not be performed or performed out of window. Treatment interruption and impacted BMD data (missing or out of visit window) due to COVID-19 will be considered as ICE #3. Hypothetical strategy, in which the interest is in the treatment effect if the ICE did not occur, is a recommended option for most pandemic-related ICEs (R. Daniel Meyer, et al., 2020).

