The data after ICE#1 and ICE#2 will be handled by treatment policy strategy and will use the observed data to do analysis. COVID-19 impacted data after ICE#3, then it will be setting to missing and imputed by multiple imputation (MI) under missing at random (MAR) assumption (MI-MAR). Details of this multiple imputation analysis are outlined in Appendix 13.4. This COVID-19 impacted data includes any BMD data after treatment interrupted (exceed 70 days since previous IMP, based on PK modeling which demonstrated that BMD loss begins after 70 days without dosing) and any missing data or out of window (exceed 70 days since previous IMP) data due to Covid-19 (other than actual COVID-19 infection). Missing data other than due to COVID-19 impacted will be imputed by LOCF.

Missing baseline BMD by DXA at any anatomical site will not be imputed and evaluated for the BMD analysis. Missing postbaseline BMD will be imputed using the LOCF approach (by carrying forward the last non-missing postbaseline value prior to the missing value from the same anatomical site) in the 6-month analysis.

In all visits and including the screening visit, if duplicated DXA assessment were performed on the same visit the mean of the duplicated BMD values will be used for analysis. The corresponding

Confidential Page 32 of 89

T-score at baseline will be converted using the mean of the duplicated BMD (checking missing DXA assessment during DEMs in section 4.2).

If a subject has BMD values from different DXA machine types (ie, Hologic and Lunar) only those BMD values that are collected from the same machine type as the Baseline BMD will be used for analyses and imputation. For anatomical sites that can be measured on different body sides (ie, left and right), only those BMD values that are collected from the same body side as the Baseline BMD will be used for analyses and imputation.

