### Sensitivity and Supplementary analyses of the primary efficacy 8.1.2 variable(s)

Sensitivity and supplementary analyses of the primary efficacy endpoint will be conducted:

Approach	Analysis Set	ICE/ICE Strategy	Missing Data Strategy
Sensitivity analysis 1	PPS	NA S	Same with primary analysis
Sensitivity analysis 2 MMRM	FAS US	Same with primary analysis	Data after ICE#3 will be setting to missing and leave missing before running MMRM. No other imputatio before MMRM.
Sensitivity 3	FAS	Same with primary analysis	Observed

Page 33 of 89

Supplementary analysis 1	FAS	ICE#1, ICE#2, and ICE#3 from the primary estimand will all be handled by treatment policy strategy in this supplemental analysis.	LOCF
Supplementary analysis 2	FAS	ICE #1: treatment discontinuation (BMD data collected >70 days after last IMP) will be handled by hypothetical strategy. ICE #2: alternative osteoporosis therapy will be handled by hypothetical strategy.	Data after ICEs will be setting to missing and replaced with LOCF
Supplementary analysis 3	FAS	Same with Supplementary analysis 2	Data after ICEs will be setting to missing and replaced with MI- MAR

For sensitivity analysis 2, a mixed effects model with repeated measures model (MMRM) will be fit with the percent change from Baseline at Months 3 and 6 in BMD of the lumbar spine as the dependent variable, and Baseline BMD, machine type at baseline, interaction of Baseline BMD and machine type at baseline, visit (categorical), treatment (categorical), interaction of treatment and visit, region and interaction of treatment and region as the independent variables. The MMRM analysis will include subject as a random effect, treatment, age strata group (stratification factor), region, visit, and treatment-by-visit interaction as fixed effects, with adjustment for baseline BMD value. The variance structure will allow for heteroskedasticity of variance between treatment groups. The FAS will be used for the repeated measurement model. If model cannot be estimated, region will be excluded from MMRM model.

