# 8.2 Statistical analysis of the secondary efficacy variables

For the secondary efficacy BMD endpoints during the DBPC Period (at total hip and femoral neck at Month 6), will be performed following the same analyses that for the primary endpoints. The main analysis and sensitivity/supplementary analyses of key secondary endpoints will follow same estimands than the primary endpoint except attribute of "Endpoint". COVID-19 related intercurrent event is also added to the estimand of key secondary endpoints and same strategy in each analysis.

- Percent change from baseline in BMD at the total hip at the end of the DBPC (Month 6) as assessed by DXA
- Percent change from baseline in BMD at the femoral neck at the end of the DBPC Period (Month 6) as assessed by DXA
- Percent change from baseline in BMD at the lumbar spine at the end of OL Treatment Period (Month 12) as assessed by DXA in subjects who are continuing with 6 months of romosozumab treatment after initially being randomized to 6 months of romosozumab treatment in the Double-Blind, Placebo-Controlled Period (for a total of 12 months of romosozumab treatment)
- Percent change from baseline in BMD at the total hip at the end of OL Treatment Period (Month 12) as assessed by DXA in subjects who are continuing with 6 months of romosozumab treatment after initially being randomized to 6 months of romosozumab treatment in the Double-Blind, Placebo-Controlled Period (for a total of 12 months of romosozumab treatment)
- Percent change from baseline in BMD at the femoral neck at the end of OL Treatment Period (Month 12) as assessed by DXA in subjects who are continuing with 6 months of romosozumab treatment after initially being randomized to 6 months of romosozumab treatment in the Double-Blind, Placebo-Controlled Period (for a total of 12 months of romosozumab treatment)
  - The derivation rules specified in Section 8.1.1 will be applied for the calculation of the secondary BMD endpoints as well.

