# 8.2.1 Secondary efficacy variables - DBPC Period

For the secondary efficacy BMD endpoints during the DBPC Period (at total hip and femoral neck at Month 6), a percent change from Baseline in DXA BMD will employ an ANCOVA model. The ANCOVA model will include the same independent variables and interactions as described in Section 8.1.1. The FAS will be used for this analysis. This analysis will be performed with adjustment for multiplicity as described in Section 4.5. Nominal (unadjusted) p-values will be provided as well for exploratory purposes.

A sensitivity analysis will be performed on the analysis of the secondary efficacy variable as described in the above paragraph based the PPS. In addition, a MMRM will be fit with the percent change from Baseline at Months 3 and 6 in BMD of the total hip and femoral neck with

the same independent variables and interactions as described in Section 8.1.1. The FAS will be used for these analyses.

For the secondary efficacy BMD endpoints at total hip and femoral neck, the following 2 further sensitivity analyses will be conducted:

Only those values are included in analysis, which were assessed during the period when subjects received IMP and does not apply to any alternative osteoporosis therapy (licensed drugs only). In particular, all values which were assessed more than 70 days after last dose of IMP or were assessed after the first intake of alternative osteoporosis therapy (licensed drugs only) will be considered as missing data and will not be imputed. For one analysis, missing data imputation via LOCF will be applied, and for the other analysis via multiple imputation according to missing at random assumption will be applied.

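### SAP Appendix 13.4 does not say which intercurrent events lead to deletion or which gaps are imputed, so read literally it could override the primary-analysis rules in SAP 8.1.1

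*SAP*

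**What the plan says.** **Primary analysis (SAP 8.1.1).** For ICE #1, "treatment discontinuation not due to COVID-19 will be handled by treatment policy strategy"; ICE #2, alternative osteoporosis therapy, has the same strategy. The section then repeats the rule for the data: "The data after ICE#1 and ICE#2 will be handled by treatment policy strategy and will use the observed data to do analysis". Only COVID-affected data (ICE #3) are set to missing and imputed under missing at random. These include "any BMD data after treatment interrupted (exceed 70 days since previous IMP", and data missing or out of window because of COVID-19. For the method, "Details of this multiple imputation analysis are outlined in Appendix 13.4". Other gaps get LOCF. SAP 3.9 states the same split: MI for COVID gaps, LOCF for the rest. A second LOCF sentence in 8.1.1 does not repeat the COVID exception.

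**Key secondary endpoints (SAP 8.2).** "The main analysis and sensitivity/supplementary analyses of key secondary endpoints will follow same estimands than the primary endpoint", apart from the endpoint itself, so total hip and femoral neck inherit these rules.

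**Analyses that delete after ICE #1 and #2.** Supplementary analysis 3 (SAP 8.1.2) treats both as hypothetical: "Data after ICEs will be setting to missing and replaced with MI"-MAR. SAP 8.2.1 has a matching total hip and femoral neck analysis. It treats values more than 70 days after the last dose, or after alternative therapy starts, as missing, and "for the other analysis via multiple imputation according to missing at random assumption will be applied".

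**Appendix 13.4.** This is the SAP's only description of MI-MAR. Step 1: "Any observation after date of ICEs will be set to missing". Step 2 covers all intermittent and monotone gaps. Step 2c truncates imputed values to a range that is never given. The MCMC pseudo-code sets `min=0 max=1` with raw baseline, Month 3 and Month 6 BMD in its variable list.

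**The concern.** One appendix appears to serve analyses that need opposite rules. The primary analysis keeps data after ICE #1 and #2. Supplementary analysis 3 and the 8.2.1 MI analysis remove them. Step 1 as worded suits the second group, yet among the MI analyses only 8.1.1 actually cites the appendix.

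The appendix holds the executable steps. If one program were written from it and shared, all three confirmatory tests could carry the supplementary estimand for ICE #1 and #2. Non-COVID gaps could also be filled by MI where 3.9 and 8.1.1 intend LOCF. What is at stake is whether the reported estimate is the treatment-policy one that the SAP describes.

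**Working it through.** The SAP gives no figure on this point. The first check is therefore of the text; the sizes after it rest on assumed rates.

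**Rules side by side**

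| Data | 8.1.1 (primary) | Suppl. analysis 3 and 8.2.1 MI | Appendix 13.4 |
|---|---|---|---|
| Observed after ICE #1 | Kept | Missing if more than 70 days after last dose | Missing; ICE not named |
| Observed after ICE #2 | Kept | Missing | Missing; ICE not named |
| COVID-affected (ICE #3) | Missing under the 70-day rule, then MI | Not stated | Missing after the ICE date; no 70-day rule |
| Other gaps | LOCF | Not separated by cause | Imputed; sorted by pattern, not cause |

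The last column differs from the primary column in every row if read literally.

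**Date of the cut.** A study month is 30 days. With a last dose at Month 4, the Month 6 scan falls 180 − 120 = 60 days later, inside the limit. With a last dose at Month 3 it falls 180 − 90 = 90 days later, outside it. After a COVID interruption 8.1.1 would keep the first scan. A cut at the date of interruption might not.

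**Size of a literal Step 1.** From SAP 2.6, the lumbar spine difference D is 6.9 (planning value) to 9.4 (study 20070337). Assumed: a share p of the romosozumab arm has an observed Month 6 scan after ICE #1 or #2; that scan shows a fraction r of the on-drug gain; the placebo mean is unaffected; MI restores the full on-drug gain. Then shift = p × (1 − r) × D.

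- p = 1%, r = 80%, D = 6.9: 0.01 × 0.2 × 6.9 = 0.014
- p = 1%, r = 40%, D = 9.4: 0.01 × 0.6 × 9.4 = 0.056
- p = 5%, r = 40%, D = 9.4: 0.05 × 0.6 × 9.4 = 0.282
- extreme, p = 10%, r = 25%, D = 9.4: 0.10 × 0.75 × 9.4 = 0.705

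Simulation (200:100, SDs 5.26 and 3.34, 400 replicates, 20 imputations by arm) gave 0.012 to 0.014 for the first case, 0.280 to 0.285 for the third and 0.696 to 0.705 for the extreme one. The planning standard error is √(5.26²/200 + 3.34²/100) = 0.50.

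Other sites, with the SAP 2.6 differences:

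- Total hip: 0.01 × 0.2 × 2.5 = 0.005 to 0.05 × 0.6 × 3.5 = 0.105
- Femoral neck: 0.01 × 0.2 × 2.0 = 0.004 to 0.05 × 0.6 × 3.2 = 0.096

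Femoral neck power, Satterthwaite t-test, SDs 4.39 and 4.10: the planned 146:73 gives 91.0% at a difference of 2.0, in agreement with the stated minimum of 90%. At 200:100 it is 97.2% at 2.0, and 97.9% at 2.0 + 0.05 × 0.6 × 2.0 = 2.06.

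**MI in place of LOCF, lumbar spine.** Assumed: a share p of romosozumab Month 6 values is missing for non-COVID reasons; the Month 3 gain is a fraction f of 6.9; placebo is flat. Shift = p × (1 − f) × 6.9.

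- p = 3%, f = 80%: 0.03 × 0.2 × 6.9 = 0.041 (simulated 0.041)
- p = 10%, f = 40%: 0.10 × 0.6 × 6.9 = 0.414 (simulated 0.419)

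**Bound of 0 to 1.** Appendix 13.4 imputes raw values, and SAP 6.2 gives BMD in g/cm². As coded, the MCMC call fills Month 3 values that are missing when Month 6 is observed; the monotone call that fills Month 6 has no bound. SAP 8.3 applies the 8.1.1 rules to Month 3 BMD, so that endpoint is affected directly. Month 6 can be reached only through bounded Month 3 values in the regression that predicts it, about 0.002 points on average in a simulation under assumed inputs. With a Month 6 gain of 6.9%, a mean Month 3 value passes 1 for a baseline above 1/(1 + 0.069 × 0.8) = 0.948 to 1/(1 + 0.069 × 0.4) = 0.973 g/cm². Individual draws can pass it at lower baselines.

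**The case against.** The strongest reply is that 8.1.1 already decides the matter. It keeps data after ICE #1 and #2, limits MI to COVID-affected data, and cites the appendix for the details of that limited MI. SAP 8.1.2 also uses an unnumbered reference to ICEs to mean those of the analysis in hand, so Step 1 can be read in the same way. The 70-day limit is part of how 8.1.1 and 8.1.2 describe the events, so the ICE date could be taken to include it. SAP 3.9 settles which gaps get MI and which get LOCF.

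Most of this stands. A programmer could go wrong only by setting 8.1.1 aside. The use of the appendix by supplementary analysis 3 is inferred from the shared MI-MAR label, and its use by 8.2.1 from a general mention of MI under missing at random; neither cites it. The direction is also conditional. The documents give no BMD response after alternative therapy, and the sign for MI against LOCF depends on the Month 3 gain being below the Month 6 gain.

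What remains is that the executable text states none of these limits, the second LOCF sentence lacks the COVID exception, and no section gives the order of MI and LOCF.

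**Conclusion.** The point holds as a specification defect that should be repaired. Step 1 and Step 2 of Appendix 13.4 conflict with 8.1.1 when followed literally, for the primary endpoint and the two key secondary endpoints.

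If post-ICE gains are lower and mainly in the romosozumab arm, a literal Step 1 would raise the lumbar spine difference by about 0.01 to 0.28 points at assumed rates of 1% to 5%. The 0.70 case needs 10% of the arm and does not fit the SAP's description of ICE #1 and #2 as rare. If the Month 3 gain is below the Month 6 gain, MI for LOCF would add about 0.04 to 0.41 points at 3% to 10% missing.

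A reader might infer more than the documents support:

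- That the primary analysis will use the wrong estimand, or has none defined. Section 8.1.1 defines it clearly.
- That the trial's conclusions are threatened. The shifts are small against a planned difference of 6.9, and femoral neck power moves by 0.7 percentage points.
- That the 0 to 1 bound distorts the primary result. It acts directly on Month 3 values, and on imputed Month 6 values only indirectly and negligibly.
- That the monotone pseudo-code, which runs by imputation with treatment as a class variable, breaks a per-arm rule. The appendix text supports both readings, so no change is asked for there.

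**What to change.** 1. **Step 1.** For the primary analysis and the matching total hip and femoral neck analyses, set only ICE #3 data to missing under the 70-day rule of 8.1.1, and keep observed data after ICE #1 and #2. Limit deletion after ICE #1 and #2, as defined in 8.1.2 and 8.2.1, to supplementary analysis 3 and the 8.2.1 MI analysis. State how ICE #3 data are handled in those two.
2. **LOCF and MI.** Restrict the second LOCF sentence in 8.1.1 to gaps not due to COVID-19, consistent with 3.9. Limit Step 2 in the primary analysis to COVID-related gaps. State the order of MI and LOCF, including what is carried forward when the Month 3 value was itself deleted for COVID-19.
3. **Bound.** Remove `min=0 max=1`, and either remove Step 2c or give a justified BMD range.

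The cost is a few lines in Appendix 13.4 and one sentence in 8.1.1, settled before the 6-month unblinding. It needs no new data and no new analysis, and leaves the stated primary estimand unchanged.
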